#### **6.0 Therapy**

Treatment will commence following the pre-treatment assessment and all participants will be then randomized and seen for an introductory session and then treated once or twice per week for 6-11 therapy sessions, including one information gathering and preparation for VRE sessions. Patients will be randomized to receive dexamethasone or pill placebo before the VRE sessions. VRE will be limited to a minimum of 6 sessions and a maximum of 11 sessions, based upon reaching criterion of 70 % symptom improvement as indicated on the PTSD Symptom Scale or an agreement between clinician and participant that maximum treatment response has been achieved. All sessions will be individual and weekly or twice weekly. The first session will last approximately 90 minutes and will be spent in information gathering, treatment planning, and explaining the treatment rationale to the patient. Information gathering will review the history of PTSD and their military service and will include a brief psychosocial history, including review of prior treatment. The VRE sessions will last 90-minutes each. During VRE sessions patients will wear a head-mounted display with stereo earphones that will provide visual and audio cues consistent with Iraqi or Afghan military scenarios. The therapist will make appropriate comments and encourage continued exposure until anxiety has habituated. During exposure, information will be gathered on the participant's anxiety level through the use of a 0-100 SUDs scale. All therapists will have been trained in Prolonged Imaginal Exposure therapy (PE) followed by training in VRE by Drs. [name] and [name]. Drs. [name] and [name] will supervise all therapy.

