#### Measures at each Therapy Session

Expectancy of Therapeutic Outcome Questionnaire (ETOQ) assesses how logical the treatment appears, and the expectancy of success for the patient and for others. This measure is administered after session 1 only.

Clinical Global Impressions Scale, Severity of Illness (CGI-Severity; Guy & Bonato, 1970). This is a study personnel rated measure of severity of illness ranging from 0 (not assessed) to 7 (among the most extremely ill patients). This measure is administered after sessions 1–6.

Clinical Global Impression – Improvement (CGI-Improvement; Guy & Bonato, 1970). This is a study personnel rated measure of patient's improvement since start of study ranging from 1 (very much improved) to 7 (very much worse). This measure is administered after sessions 2-6.

Clinical Global Improvement Scale, Patient Report (CGI - Self Report; Guy & Bonato, 1970). This is a self-reported global measure of change in severity of symptoms, ranging from 1 (*very much improved*) to 4 (*unchanged*) to 7 (*very much worse*). This measure is administered after sessions 1-6.

The PTSD Symptom Scale is a 17-item interview used to aid in the detection and diagnosis of PTSD (described above), administered before sessions 2-6.

Subjective Units of Discomfort (SUDs) will be gathered during each exposure session (sessions 2-6). Participants will be asked to rate their level of discomfort on a scale of 0 (no anxiety) to 100 (panic levels of anxiety) every 5 minutes during the VR exposure.

Intent to Attend (Leon et al., 2007) is a short, two question survey asking participants how likely they are to complete all of the study and how likely they are to attend the next session.

Blinded Medication Check is a one-question measure to assess which medication the participant believes they took.

Cortisol Sampling will be obtained from saliva in order to measure post-dexamethasone cortisol levels and detect the presence of dexamethasone in saliva. Cortisol sampling methods are described below.

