### Interventions:

VRE. The VRE treatment program will consist of 90-minute individual treatment sessions. Procedures include education about common reactions to trauma, breathing retraining, prolonged (repeated) virtual exposure to trauma, and discussion of thoughts and feelings related to exposure exercises. The discussion addresses unrealistic beliefs about the self and the world, attempting to “process” material that came up during the exposure and make new associations explicit (e.g., “You see, by staying with the image long enough, your anxiety decreases.”) Session 1 is devoted to information gathering, education about common reactions to trauma, elaboration of the index trauma, breathing retraining, and fostering a therapeutic alliance. The remaining 5-10 sessions consist of VRE interventions and discussion of these experiences.

The patient will be encouraged to expose him or herself to traumatic memories triggered by the virtual environments, following guidelines for standard exposure therapy. As the number of sessions is limited, we are limiting exposure to the identified index trauma, and in some cases, a second traumatic event. The therapist asks the patient to give a SUDs (Subjective Units of Discomfort, 0= no anxiety and 100=maximum anxiety) rating approximately every five

minutes during all exposures as an indication of his level of anxiety. The therapist makes appropriate comments and encourages continued exposure until anxiety has decreased. The therapist simultaneously views on a video monitor all of the virtual environments in which patients are interacting and therefore is able to comment appropriately and is attempting to match stimuli that the patient is describing to the virtual stimuli, as much as possible, for example by landing the helicopter at the appropriate time in the memory, or by having gunfire, bombs, fog, or night time to match the memory. The 90-minute session will consist of 15 minutes of checking in with the patient about their functioning and anxiety since the last session, up to 45 minutes of exposure to their traumatic memories and the virtual stimuli, followed by processing and discussion about the material from the exposure. Information is gathered each session on any other exposure the patient may have conducted, although no homework will be assigned, as patients will only be on study medication for office visits.

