Medication. Beginning with session 2 (the first session where VRE is used), the patients will take either the dexamethasone medication (0.5 mg) or placebo 8-10 hours prior to the VRE session. A study staff member will call the patient to remind them to take their medication at the appropriate time. As the study will be double-blind, neither the patients, the study staff nor clinicians will know which pill the patient took. However, as a check for compliance, saliva samples will be tested for the presence of dexamethasone. These results will be available to investigators once the study is completed and unblinded. This approach has been used in our previous IRB protocols (IRB #51911, PI: [name]), with high compliance rates.

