## 10.0 Statistical Considerations

### 10.1 Preliminary Analyses

Premature Termination. Patients will be considered dropouts (a) if they miss two or more sessions or (b) if serious adverse reactions or clinical complications (e.g., suicidal intention) develop. Initial data analyses will be conducted on treatment completers. This will address relative efficacy among treatment completers. A second analysis will be conducted including all patients who initiate treatment using an intent-to-treat analysis. This will address relative efficacy in the population intended for treatment, thus incorporating issues related to potential differential dropouts in the treatment groups. Finally, analyses will be conducted to see if treatment completers differ from drop-outs on demographic variables and pre-treatment measures.

Group Equivalence. We will evaluate the effectiveness of random assignment to two treatment groups by comparing the groups on demographics, baseline measures of key outcome variables, and other important theoretical covariates. We will characterize differences between study dropouts and completers, and between dropouts from the VRE+DEX and VRE+placebo groups. We will compare dropouts to completers on the same set of baseline variables that will be used to examine initial group equivalence. Differences between conditions will be assessed using one way ANOVA for continuous variables and chi-square analyses for categorical variables (Fleiss et al., 2013). Any observed differences that approach statistical significance ( $P \leq 0.15$ ), and which are theoretically or empirically identified as potential confounders will be included as covariates in subsequent cross sectional and longitudinal analyses.

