### 10.2 Statistical Analyses

#### Power and Sample Size

Power calculations are based on Cohen (1992). We set the Type I Error rate at 0.05 (two-tailed) for all computations. We first calculated the number of participants needed to test the effect of VRE augmentation with DEX at immediate post-treatment assessment (Hypothesis 1 above). Then, knowing how many participants would be needed at the end of this phase, we worked backward to calculate how many participants would need to be enrolled initially. We will continue to collect data from all participants, including those who drop out of treatment or are discontinued. Thus, loss to the study represents a failure to participate in measurement, and not merely dropout from treatment. We assumed that: (1) 10% of participants will be lost to the

study by the end of treatment; an additional 15% of participants will drop out of treatment, resulting in 25% of participants randomized to placebo or 0.5mg DEX groups that would not complete treatment. We anticipate that 10% of completers will be lost to the study prior to the 3 month follow-up visits.

The effect size measure used,  $d$ , represents the standardized difference between sample means. Cohen (1988) has proposed that  $d = .30$ ,  $.50$ , and  $.80$  be categorized as “small,” “medium,” and “large,” respectively. We assume that a medium effect size—half a standard deviation—is the smallest clinically meaningful difference between DEX-augmented VRE vs. placebo-augmented VRE at the end of treatment.

For a two-group study design, 100 participants ( $n=50$  in each group) would be needed to achieve a minimum desired power of 85% to detect an effect size of  $.65$  with a 2-sided test at a significance level of 0.05.

Hypothesis 1: Patients who receive VRE+DEX will evidence more improvement on within-session measures (SUDs), on immediate post-treatment symptoms measures and on startle, SCR and HR, than the group who receives placebo.

To analyze pre-treatment and immediate post-treatment differences, the first analysis will compare the VRE+DEX condition to the VRE+placebo condition on the following outcome measures: 1) symptom measures (continuous variables); 2) psychophysiological measures (startle responses, cortisol levels, heart-rate, skin conductance) (continuous variables). It is expected that VRE+DEX participants will show significant improvement on all outcome measures immediately post-treatment compared to VRE+ placebo participants.

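### Randomising before an introductory session common to both arms counts patients who leave before the first pill as dropouts and can dilute the intent-to-treat analysis

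*Combined protocol and SAP*

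**What the plan says.** - **Order of events.** Under 6.0 Therapy, after the pre-treatment assessment "all participants will be then randomized and seen for an introductory session".
- **Content of session 1.** Under 8.0, Interventions: "Session 1 is devoted to information gathering, education about common reactions to trauma, elaboration of the index trauma, breathing retraining". It involves no pill and no virtual exposure, and nothing in it depends on allocation.
- **First difference between arms.** Same heading, Medication: "Beginning with session 2 (the first session where VRE is used), the patients will take either the dexamethasone medication (0.5 mg) or placebo".
- **Dropout rule.** Under 10.1: "Patients will be considered dropouts (a) if they miss two or more sessions", or if serious adverse reactions or clinical complications develop. Neither limb requires a pill or an exposure session to have taken place.
- **Analysis sets.** Section 10.1 analyses treatment completers first. Then: "A second analysis will be conducted including all patients who initiate treatment using an intent-to-treat analysis". Initiation is not defined.
- **Use of dropout as an outcome.** Hypothesis 1 in section 2 (Objectives) predicts fewer dropouts with DEX and explains this as patients tolerating exposure better. Section 10.2 plans to look at the number of dropouts under the same prediction.
- **Planned losses.** Under Power and Sample Size, "10% of participants will be lost to the" study by the end of treatment and a further 15% leave treatment, "resulting in 25% of participants randomized to placebo or 0.5mg DEX groups that would not complete treatment". Measurement is to continue after treatment dropout.

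**The concern.** Between randomisation and the first pill the two arms receive the same care. A patient who leaves in that window says nothing about DEX or about tolerance of exposure. Two parts of the plan are nevertheless affected.

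1. **Dropout comparison.** Such a patient goes on to miss two or more sessions and so meets the dropout rule. Leavers of this kind add similar numbers to both arms and blur the contrast that Hypothesis 1 predicts.
2. **Second analysis.** If attending session 1 initiates treatment, never-dosed patients who are still measured enter the intent-to-treat comparison with no possible drug effect. If initiation means the first pill, randomised patients are removed from an analysis labelled intent-to-treat. The plan does not say which is meant.

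**Working it through.** **1. The plan's own figure.** Inputs from Power and Sample Size: d = 0.65, two-sided alpha 0.05, power at least 85%, 50 per group, 10% lost to measurement. For a two-sample t-test the noncentrality is d × √(n/2). Power of 85% needs 43.5, so 44 per arm, or 88 in total. Allowing for loss, 88 / 0.90 = 97.8, so 98, against 100 stated. Equivalently, 50 × 0.90 = 45 measured per arm gives 86.2%. The stated size is reproduced.

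**2. Dilution of the second analysis.** The share e who leave before the first pill is not in the documents; I assume 2%, 5% and 10%. Further assumptions: 0.65 is the effect in dosed patients, leavers have no drug effect, e is equal in both arms, and leavers are measured at the same 90% rate as others.

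- Current order: d = 0.65(1 − e) with n = 45, so the noncentrality is multiplied by (1 − e).
- Randomising after session 1, consents capped at 100: d = 0.65 with n = 45(1 − e), so the noncentrality is multiplied by √(1 − e).

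| e | Current order: d, n per arm | Power | After session 1: d, n per arm | Power | Gain (points) |
|---|---|---|---|---|---|
| 0 | 0.65, 45 | 86.2% | 0.65, 45 | 86.2% | 0 |
| 2% | 0.637, 45 | 84.8% | 0.65, 44.1 | 85.5% | 0.7 |
| 5% | 0.6175, 45 | 82.6% | 0.65, 42.75 | 84.4% | 1.8 |
| 10% | 0.585, 45 | 78.4% | 0.65, 40.5 | 82.4% | 4.0 |

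The right-hand power figures are a best case. They assume that every leaver goes before session 1 ends. Someone who attends session 1 and leaves before taking the pill would still be randomised.

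**3. Sensitivity to whether leavers are measured.** Hold 45 measured per arm in total. With measurement rate m among leavers, 50 × e × m of the 45 are leavers. At m = 0.5 the gain is about 0.4, 1.0 and 2.0 points for e = 2%, 5% and 10%. At m = 0 both orders give 86.2% and the gain is zero.

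**4. Dropout comparison (illustration).** Assume 25% dropout on placebo (the plan's overall non-completion figure) and that DEX halves only the dropout that follows the first pill. Under the current order the rates are 0.25 and e + (0.25 − e)/2, with 50 per arm. Counting from the end of session 1 they are q = (0.25 − e)/(1 − e) and q/2, with 50(1 − e) per arm. Power is Φ[(difference − 1.96 × SE pooled) / SE unpooled].

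| e | Current order | Power | Counted after session 1 | Power |
|---|---|---|---|---|
| 0 | 25% v 12.5% | 36% | 25% v 12.5% | 36% |
| 2% | 25% v 13.5% | 31% | 23.5% v 11.7% | 33% |
| 5% | 25% v 15% | 24% | 21.1% v 10.5% | 29% |
| 10% | 25% v 17.5% | 15% | 16.7% v 8.3% | 22% |

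This comparison is weak in any case, and early leavers weaken it further.

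**The case against.** Randomising after baseline assessment is a legitimate choice, and several of the objections to this point hold.

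- **The first-listed analysis is not touched.** Never-dosed leavers are not completers. The power section does not name its analysis set, so it cannot be said that the powered comparison is diluted; only the second analysis can be.
- **The power gain is conditional.** People who quit after at most one session may well be among the 10% lost to measurement, and then there is no gain.
- **The top of the range is high.** A 10% rate would put 10/25 = 40% of all expected non-completion before the first pill. At 2-5% the gain is under 2 points.
- **A lighter remedy exists.** Splitting dropouts at the first pill clears up the tolerance comparison without moving randomisation.

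Stronger readings are tempting but unsupported:

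- A reader might infer bias between arms. The trial is double-blind and session 1 does not depend on allocation, so early leaving should differ only by chance.
- A reader might infer that these patients certainly enter the intent-to-treat set. Section 6.0 has treatment commence after the pre-treatment assessment and counts the information-gathering session among the therapy sessions, which favours that reading, but 10.1 does not settle it.
- A reader might say that they received no VRE at all. The Interventions text makes session 1 part of the VRE programme; what they miss is the pill and the virtual exposure.
- A reader might see harm to the expectancy questionnaire (ETOQ), since "This measure is administered after session 1 only" and so follows randomisation. It precedes any pill, under blinding, and no passage plans it as a covariate, so the harm is negligible.

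What the objections leave standing is the dropout comparison. The rule counts patients who never met the exposure whose tolerance is being tested, whatever their number.

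**Conclusion.** The point holds as a loss of efficiency and interpretability. The mismatch between the dropout rule and the tolerance hypothesis follows from the text alone. Dilution of the second analysis rests on the reading that session 1 initiates treatment, on leavers being measured, and on 0.65 being the effect in dosed patients. If 0.65 was meant as the average over everyone measured, it already allows for such leavers.

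Under those assumptions, with 2-10% leavers, power falls from 86% to 85-78%. Moving randomisation recovers it to at best 85-82%, a gain of 0.7 to 4.0 points, roughly half that if half the leavers are measured, and none if none are. The actual leaver rate is unknown. The change is worth making because it costs little.

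**What to change.** **Preferred.** In 6.0 and 8.1, place randomisation at the end of session 1, before the first study pill is dispensed. In 10.1, define the intent-to-treat set as all randomised patients. In 10.2, count dropouts for the between-arm comparison from randomisation so placed.

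**Cost.** Amendment wording, and an allocation procedure that is ready when session 1 ends. Slightly fewer than 100 may be randomised if consents stay capped at 100; to randomise 100 at a 5% or 10% leaver rate would take 100/0.95, so 106, or 100/0.90, so 112, enrolled. Results would apply to patients who attend session 1.

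**If the order must stay.** Keep an analysis of all randomised patients, report dropouts before and after the first pill separately by arm, and test the tolerance hypothesis on the latter. This costs only wording. It clarifies the dropout comparison but leaves any dilution of the intent-to-treat analysis in place.

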#### Post treatment and 3, 6 and 12-month Follow-up Assessments

The Clinician Administered PTSD Scale (CAPS) (see above).

The Beck Depression Inventory (BDI) as above.

The PTSD Symptom Scale as above.

The Clinical Global Improvement Scale (Severity, Improvement, and Patient Report) as described above.

The Quality of Life Inventory as above.

The State Trait Inventory as above.

Patient Update Interview: This a brief study personnel-interview administered to obtain general patient follow-up data, i.e. between-assessment treatment, medication changes, substance use status/changes, and patient report on relationship/employment/health changes.

Psychophysiological Patient Report as above.

Psychophysiological and Cortisol Reactivity (as described above) to the VR scenes will be assessed at each follow-up point.

Posttraumatic Stress Disorder Checklist (PCL) as above.

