### **8.1 Procedure**

Study staff will conduct extensive phone screening to determine appropriateness of this project for each patient and will provide information on project design and procedures. Upon medical history review and a physical exam performed by the study physician, a pre-assessment visit will be scheduled at which time patients will be thoroughly evaluated as to inclusion and exclusion criteria (detailed above) and explained the procedures of the project in detail. Informed consent will be obtained at this pre-assessment visit. The consent form, CAPS and M.I.N.I. will be completed prior to official study entry. If eligible and willing to participate, individuals will officially be enrolled in the study and will complete the pre-treatment assessment questionnaires. During the pre-assessment visit we will collect a one-time saliva sample to be used for the purpose of DNA extraction. DNA extraction is optional and will be presented to participants under a separate consent. Following consent, initial diagnostic interviews, self-reports, and DNA extraction (if consented), psychophysiological data will be collected (described above), including 3 cortisol samples at each assessment, and the first of the therapy visits will be scheduled. Following randomization, the participant will receive a pill and be instructed to take it at 11pm before every VRE therapy session. During any visit after taking dexamethasone, the participants will be assessed for adverse effects of the drug by the study staff. Significant adverse effects will be reviewed by the study physician; if the study physician determines that the study puts the participant at undue risk, their participation will be stopped.

All treatment will be free of charge to the participant and no funding is available to compensate for these visits (treatment sessions 1-6 or 11). Post treatment and follow-up visits, however, (post, 3, 6, and 12-month follow-up) will be compensated \$20 for time and travel.

If the treating therapist makes a clinical judgment at the conclusion of treatment sessions that a participant requires additional follow-up treatment sessions for stabilization, these may be offered as compassionate care. The participant will also continue with scheduled post-treatment assessments as per the study protocol.

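### Treatment can run to session 11 on a 70% PTSD Symptom Scale criterion, but the scale is scheduled during treatment only before sessions 2-6, so past session 6 no scheduled reading can trigger the criterion

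*Combined protocol and SAP*

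**What the plan says.** **Stopping rule (Section 6.0, Therapy).** Treatment lasts 6 to 11 sessions, once or twice a week. Within that range its length is set by "a maximum of 11 sessions, based upon reaching criterion of 70 % symptom improvement as indicated on the PTSD Symptom Scale", or by agreement between clinician and participant that the maximum response has been reached.

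**Number of exposure sessions (Section 8.0, Interventions).** Session 1 is preparatory. "The remaining 5-10 sessions consist of VRE interventions and discussion of these experiences". One study pill precedes each exposure (VRE) session, starting with session 2.

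**In-treatment schedule (Section 8.0, Measures at each Therapy Session).** The PSS entry reads "diagnosis of PTSD (described above), administered before sessions 2-6". For CGI-Improvement, "This measure is administered after sessions 2-6". CGI-Severity and the CGI self-report also end at session 6. The entry for SUDs (discomfort ratings) equates the exposure sessions with sessions 2-6.

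**Other PSS readings.** The scale is given at pre-treatment. The post-treatment and follow-up list has "The PTSD Symptom Scale as above". No section schedules it before sessions 7-11.

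**Use in the analysis.** Section 2 (Objectives) predicts fewer sessions to a 70% symptom reduction with dexamethasone. Section 10.2 will look at the number of sessions to 70% improvement or maximum treatment response.

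**The concern.** A stopping rule based on a score needs a score at each point where the rule can act. Here the rule can act from session 6 to session 11, and the scheduled readings end before session 6.

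Two things are at stake. First, beyond session 6 the length of treatment, and with it the number of study pills, is not governed by the measured half of the rule. Second, sessions to 70% is a named prediction, and for anyone treated beyond session 6 the scheduled data cannot say at which session 70% was first reached. Agreement that the maximum response has been reached yields a session count, but it does not measure a 70% reduction.

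**Working it through.** The plan gives no figure for this point. The sample size of 100 does not depend on it.

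**1. Schedule against sessions.** Session n holds VRE session n-1, so a PSS before session n reflects VRE sessions up to n-2. Readings before sessions 2-6 therefore fall after VRE 0 to 4. VRE can occupy sessions 2-11, which is 10 sessions; 5 have a scheduled PSS beforehand (2-6) and 5 do not (7-11). Decisions to continue fall after sessions 6, 7, 8, 9 and 10, and none is followed by a scheduled in-treatment reading.

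**2. What can be dated.** Take a participant below 70% before session 6 who stops at session s and is at 70% at post-treatment. The candidates are VRE sessions 5 to s-1, a count of s-5:

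| Last session s | 6 | 7 | 8 | 9 | 10 | 11 |
|---|---|---|---|---|---|---|
| Candidate VRE sessions | 1 | 2 | 3 | 4 | 5 | 6 |

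A stop at session 6 loses nothing. Sessions 6 to 11 span 5 gaps: 5 × 0.5 = 2.5 weeks at twice weekly, 5 × 1 = 5 weeks at weekly, plus the time to post-treatment.

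**3. Illustration.** Assumptions, none from the documents: a constant chance p per VRE session of first reaching 70%; nobody stops by agreement; everyone below 70% before session 6 continues to session 11. With S(j) = (1-p)^j:

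- Share of those reaching 70% by VRE 10 who do so after VRE 4: 1 - (1-S(4))/(1-S(10)).
- Mean VRE sessions to 70%, capped at 10: the sum of S(0) to S(9). S(5) to S(9) are known only to lie between S(10) and S(4), so the mean is uncertain by 5 × (S(4)-S(10)).
- Participants spared sessions if a reading of 70% made the coming session the last: reaching 70% after VRE k = 5 to 8 saves 9-k sessions, with probability S(4)-S(8) overall.

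| p | Undated share | Width of mean | Spared | Mean sessions spared |
|---|---|---|---|---|
| 4% | 55% | 0.92 | 13% | 2.55 |
| 8% | 50% | 1.41 | 20% | 2.60 |
| 12% | 45% | 1.61 | 24% | 2.66 |
| 20% | 34% | 1.51 | 24% | 2.78 |

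At p = 8%, S(4) = 0.7164, S(10) = 0.4344 and S(0) to S(4) sum to 4.261. The mean lies between 4.261 + 5 × 0.4344 = 6.43 and 4.261 + 5 × 0.7164 = 7.84; the true value is 7.07.

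The spared share is an upper limit. With an assumed 10% to 30% chance per session of stopping by agreement, from VRE 5 on, it falls to 4% to 17%.

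**4. Between-arm comparison.** Assume a hazard ratio of 2.0, so the faster arm has 1-(1-p)². At p = 8% this is 1 - 0.92² = 15.4%. The true means are 7.07 and 5.28, a difference of 1.79. Dating every undated response as early as possible gives 6.43 - 4.63 = 1.80 (1.81 before rounding). Dating every one as late as possible gives 7.84 - 6.25 = 1.59.

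Power by simulation, with 45 per arm (50 less the 10% loss in Section 10.2), two-sided 0.05, and a log-rank test (a test of two proportions for the last column):

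| p | Every session dated | Pre-session 2-6 plus post-treatment | Post-treatment status alone |
|---|---|---|---|
| 4% | 58% | 57% | 55% |
| 8% | 77% | 76% | 73% |
| 12% | 84% | 81% | 74% |
| 20% | 88% | 85% | 54% |

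Using the scheduled readings together costs about 1 to 4 points. Post-treatment status alone can cost far more.

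**The case against.** The strongest reply is that nobody chose to stop measuring at session 6. The rule itself presupposes a reading, and the section heading promises measures at each session. SUDs are limited to sessions 2-6 in one place yet taken "during all exposures as an indication of his level of anxiety" in another, and Section 8.1 writes "treatment sessions 1-6 or 11". All this suggests ranges that were not updated when the course was lengthened. That explanation is probably right, and nothing in the documents forbids a PSS after session 6. A reader might infer that the sponsor meant to leave the criterion unmeasured; the text does not support that. But the entries under that heading carry their own ranges, one of them for session 1 only, so the heading cannot override them. Staff and database forms would follow the ranges.

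Four further points limit the concern:

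- Treatment past session 6 can end in other ways than agreement or the cap. Section 8.1 allows a stop for undue risk, and Section 10.1 defines dropout by missed sessions or serious adverse reactions.
- The PSS asks about the past month, and the gap of 2.5 to 5 weeks is about one recall period. Extra readings would sharpen the dating but not make it exact.
- The magnitudes in step 3 rest on assumed rates and switch off the agreement route that the plan provides.
- This is a pilot with exploratory aims, and Section 10.2 names no test for the session count.

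These reduce the size of the problem. They do not supply the missing readings.

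**Conclusion.** The inconsistency is in the current text and should be corrected. Followed as written, no scheduled reading can trigger the 70% criterion past session 6, and for those treated longer the session of first reaching 70% is known only to lie in an interval of 2 to 6 VRE sessions. Both statements follow from the schedule alone. The undated share, the width of the mean and the sessions spared depend on the assumptions in step 3.

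Two stronger conclusions might be inferred and are not supported. One is that the sessions-to-70% comparison is lost or badly underpowered: with the pre-session 2-6 and post-treatment readings combined and one dating rule in both arms, the effect is small under the rates tried. The other, in the opposite direction, is that the post-treatment PSS alone is enough: at p = 20% it gives about 54% power against 88%. Participants who stop at session 6 are unaffected, and the sample size does not change.

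**What to change.** - **Section 8.0, Measures at each Therapy Session:** schedule the PSS before every session from 2 through the last session held, up to 11. Correct the SUDs range to match the Interventions text. Extending the CGI ratings is optional, since they are not the stopping criterion.
- **Section 6.0:** state which reading triggers stopping. For example: *if the PSS before session n (n = 6 or later) is at least 70% below baseline, session n is the last.*
- **Section 10.2:** report sessions to a 70% PSS reduction separately from stopping by agreement. Count completed VRE sessions before the first PSS at least 70% below baseline, with the post-treatment PSS as the reading after the last session. Treat a stop by agreement without 70% as a competing event, or as not reached by the cap. Ordinary censoring would be informative: it would give people judged to have reached their maximum response the same future chance of 70% as those who continue.

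**Cost:** up to 5 more brief PSS interviews per participant, only for those who continue past session 6 and at visits already planned, plus protocol wording and database forms for sessions 7-11. Dating stays approximate because of the one-month recall.
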